7.4 Sample Size

The sample size per treatment group is arbitrarily determined to be 25 evaluable patients within the two-year study period. Approximately 50 patients are planned to be enrolled to complete the study.

The design of this study was compared between the two groups. The main evaluation index (O'Leary-Sant score) was set to 8.0 decreased in the treatment group, 5.0 decreased in the control group, SD = 5.0, α = 0.05, power= 0.80, and the total sample size was analyzed by computer:

The sample size of this study is about 25 people in each group, at least 50 people need to reach statistical significance.

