4. SUBJECTS

4.1. Number and Source

Approximately 50 patients will be enrolled and be completed within the two-year study period.

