5.2. Study Visits and Evaluations

5.2.1. Screening Visit (2 weeks before the treatment day)

5.2.1.1 Explain the nature of the study and have patients to read and sign an Informed Consent Form.

5.2.1.2 Screen patients for inclusion/exclusion criteria (section 4.2 and 4.3).

5.2.1.3 Medical History of IC/BPS and previous treatment modalities.

5.2.1.4 Vital signs monitoring and general physical examinations of all systems, EKG examination to rule out abnormal cardiac diseases, and biochemistry examinations including CBC, PT, APTT, ALT, AST and Cr.

5.2.1.5 Check Uroflowmetry and record, maximum flow rate, voided volume and PVR volume.

5.2.1.6 Urinalysis for WBC, RBC, PH, Protein, Glucose, Bacteria if patient has symptoms suggestive of urinary tract infection.

5.2.1.7 Physical assessments to exclude bladder outlet obstruction or bladder pathology.

5.2.1.8 Record concomitant medication.

5.2.1.9 Dispense three-day voiding diary to record for 3 days before the treatment day.

5.2.1.10 Record O'Leary-Sant symptom score, VAS.

5.2.1.11 Discontinue all previous IC-related medication.

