5.3. Withdrawal Criteria

Patients with any of the following conditions may be withdrawn from the trial:

- 5.3.1. Patients decide to withdraw their consent at any time-point.
- 5.3.2. Patients indicate the status of lack of efficacy which is of clinical significance judged by the investigators that may lead to permanent damage to the patients.
- 5.3.3. Investigators consider that there is of safety concerns for the patients to remain in the trial (such as development severe medical disease).
- 5.3.4. Lost of follow-up or death.

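### The target of 25 evaluable patients per group equals planned enrolment, with no allowance for loss, so it is unlikely to be met if about 50 are randomised

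*SAP*

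**What the plan says.** SAP 7.4 fixes the size in evaluable patients: "The sample size per treatment group is arbitrarily determined to be 25 evaluable patients within the two-year study period". It then gives the recruitment figure: "Approximately 50 patients are planned to be enrolled to complete the study". Protocol 4.1 has the same number: "Approximately 50 patients will be enrolled and be completed within the two-year study period". SAP 7.4 closes by treating 50 as a floor: "The sample size of this study is about 25 people in each group, at least 50 people need to reach statistical significance".

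The planning inputs in SAP 7.4 are a score that "was set to 8.0 decreased in the treatment group, 5.0 decreased in the control group", with "SD = 5.0, α = 0.05, power= 0.80".

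The plan expects some patients to leave. Protocol 5.3 lists four kinds of reason for withdrawal: withdrawn consent ("Patients decide to withdraw their consent at any time-point"), lack of efficacy, safety concerns, and loss to follow-up or death. SAP 7.3 says incomplete observations stay missing and are not estimated. Neither document states an expected loss rate, an inflation of the sample size, or a rule on replacing withdrawn patients. Neither defines *enrolled* or *evaluable*. SAP 7.1 is headed Evaluability but defines only the ITT and PP populations and does not say which one the 25 refers to.

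**The concern.** One number, 50, does two jobs. It is the least that must be evaluable and roughly the most that will be enrolled. The two agree only if essentially nobody is lost between randomisation and the 1-month visit (V6).

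The primary comparison is an ANOVA on the change in O'Leary-Sant score, and missing scores are not estimated. Each patient without a 1-month score is therefore one fewer in that analysis. A reader of SAP 7.4 would expect 25 scores per group and would probably see fewer, with a wider confidence interval and lower power than at 25. Sites also cannot tell from the text whether recruitment stops at 50 randomised or at 50 completed.

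**Working it through.** **Inputs.** From SAP 7.4: 25 evaluable per group, about 50 enrolled, difference 8.0 − 5.0 = 3.0, SD 5.0, α = 0.05. SAP 7.2 makes all tests two-tailed, and Protocol 3 gives 1:1 allocation. Between two groups, the ANOVA of SAP 7.2 is the two-sample t-test. **Assumed:** loss before V6 of 5%, 10%, 15% or 20%, equal in both groups, because the documents give no rate.

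**Step 1: the plan's own figure.** Evaluable target: 2 × 25 = 50. Planned enrolment: about 50. Implied allowance for loss: 50 − 50 = 0.

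The stated inputs do not give 25 per group. The normal formula 2 × [(1.960 + 0.842) × 5.0 / 3.0]² gives 43.6, so 44 per group; the t-test gives 44.6, so 45. With 25 per group the standardised difference is 3.0 / 5.0 = 0.6 and t-test power is 54.7%, not 80%. That is a separate defect. It matters here because 54.7%, not 80%, is the baseline against which loss must be judged.

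**Step 2: effect of loss when 50 are randomised.**

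- Remaining per group: n = 25 × (1 − loss)
- Standard error of the difference: 5.0 × √(2/n)
- Ratio to the standard error at 25: 1/√(1 − loss)
- Power: two-sided t-test, non-centrality 0.6 × √(n/2), 2n − 2 degrees of freedom

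| Assumed loss | n per group | SE of difference | SE ratio | 95% CI half-width | Power |
|---|---|---|---|---|---|
| 0% | 25 | 1.41 | 1.00 | 2.84 | 54.7% |
| 5% | 23.75 | 1.45 | 1.03 | 2.92 | 52.6% |
| 10% | 22.5 | 1.49 | 1.05 | 3.01 | 50.3% |
| 15% | 21.25 | 1.53 | 1.08 | 3.10 | 48.0% |
| 20% | 20.0 | 1.58 | 1.12 | 3.20 | 45.6% |

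The half-width is the t quantile times the SE; at 10% loss it is 2.017 × 1.491 = 3.01.

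**Step 3: chance of no loss at all.** If exactly 50 are randomised and losses are independent, the chance that all 50 give a 1-month score is (1 − loss)^50: 0.95^50 = 7.7% and 0.90^50 = 0.5%.

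**Step 4: numbers needed to keep 25.** With 25/(1 − loss) rounded up, the number to randomise is 27, 28, 30 or 32 per group at 5%, 10%, 15% or 20% loss. This preserves the 25 but not 80% power. Starting from 45 per group, 10% loss would need 45/0.90 = 50 per group.

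**The case against.** The strongest case on the other side is that the text is loose rather than wrong. Enrolment is only approximate, and Protocol 4.1 speaks of patients enrolled and completed, which can be read as 50 completers with 50 as a floor. This stands as far as it goes: a reader might infer that the target *will* be missed, and the documents do not support that. But if 50 completers are meant, the number to randomise is stated nowhere, and the same gap remains.

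A second defence is that *evaluable* may mean the ITT population of SAP 7.1, which requires only baseline screening and treatment. A patient lost after treatment would then still count. That keeps the label but not the analysis, because under SAP 7.3 a treated patient without a 1-month score adds nothing to the ANOVA.

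The effect is also modest. At 5% to 10% loss, power falls only from 55% to between 53% and 50%, and V6 is about seven weeks after the first treatment. The shortfall from 80% to 55% in the same section is much larger. Both points are fair and limit the weight of this one.

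Three further inferences are tempting but unsupported:

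- *Screen failures use up the 50.* At the screening visit, staff "have patients to read and sign an Informed Consent Form" before the criteria are checked. Under Protocol 5.2.2, however, a randomisation number goes only to a patient confirmed eligible at V1. Screen failures would count only if *enrolled* meant consented, which neither document says.
- *Per-protocol exclusions reduce the 25.* SAP 7.1 bases the primary conclusions on ITT, and nothing ties the 25 to the PP set.
- *Sites will replace drop-outs out of sequence.* Replacement is not mentioned, and Protocol 3.1 assigns numbers in the order in which patients become eligible.

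**Conclusion.** The point holds in a limited form. The evaluable target equals planned enrolment, no allowance for loss is stated, and *enrolled* and *evaluable* are undefined. If about 50 are randomised, 25 per group with a 1-month score is unlikely, though not impossible. The size is 23.8 down to 20.0 per group, standard errors 3% to 12% larger, and power of 53% down to 46% against 55% at a full 25.

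These figures rest on assumed loss rates of 5% to 20%, equal loss in the two groups, and the plan's own difference and SD. The point is separate from the question of whether 25 per group gives the stated power, but both should be corrected together. A loss allowance added to 25 would leave the 80% claim wrong, and a corrected base size would still need an allowance.

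**What to change.** Restate Protocol 4.1 and SAP 7.4 as follows:

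1. About 50 patients will be randomised; use that word in place of *enrolled*.
2. *Evaluable* means having a 1-month O'Leary-Sant score.
3. State an assumed loss rate and the evaluable number it implies. At 10% this is about 22 to 23 per group, with a 95% confidence interval of about ±3.0 points on the difference if the SD is 5.0. The sponsor should supply the rate; 10% is only an illustration.
4. State whether withdrawn patients are replaced.
5. In the same edit, replace the 80% power figure in SAP 7.4 and the sentence that at least 50 suffice with the power the expected number delivers, about 50% at 10% loss. Otherwise the section would contradict itself more openly than it does now.

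The cost is wording only: no visit, procedure or randomised number changes. The downside is that the stated figures become less favourable. If the sponsor prefers to keep 25 evaluable per group, Step 4 gives the numbers to randomise, but that means recruiting more patients and still leaves power at about 55%.

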- (2) The abnormalities of laboratory test results will be reported by patient list in the patients who have been tested for having severe adverse event.
- (3) The changes in physical examinations will be presented in the by-patient list.
- (4) All statistical tests used will be two-tailed with α = 0.05.

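### The sample size does not follow from its own inputs: 25 per group gives about 55% power for the primary comparison, not the stated 80%

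*SAP*

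**What the plan says.** SAP section 7.4 explains the sample size in two ways. It first presents the number as a choice: "The sample size per treatment group is arbitrarily determined to be 25 evaluable patients within the two-year study period". It then presents the same number as the result of a computer calculation for a comparison of the two groups, with the main index "set to 8.0 decreased in the treatment group, 5.0 decreased in the control group, SD = 5.0, α = 0.05, power= 0.80". The conclusion is: "The sample size of this study is about 25 people in each group, at least 50 people need to reach statistical significance".

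Three other places fix the remaining inputs:

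- SAP section 7.2 sets the sidedness: "All statistical tests used will be two-tailed with α = 0.05". It also specifies ANOVA on the net changes for the between-group comparison.
- Protocol section 3 sets 1:1 allocation to LESW or placebo.
- Protocol section 4.1 sets enrolment: "Approximately 50 patients will be enrolled and be completed within the two-year study period". This equals twice the evaluable number, so nothing is added for loss.

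**The concern.** The planned difference is 8.0 − 5.0 = 3.0 points against an SD of 5.0, a standardized effect of 0.6. An effect of that size normally needs well over 25 patients per group for 80% power, so the stated number looked too small for its own assumptions.

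The stake is how the primary result will be read. A plan that claims 80% power invites readers to take a non-significant result as evidence against efficacy from an adequately powered trial. If the true power is near one half, that reading is unsafe. The closing sentence of section 7.4 adds to the problem by suggesting that 50 patients suffice for significance, which no sample size can promise.

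**Working it through.** **Inputs**

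| Input | Value | Source |
|---|---|---|
| Difference in mean decrease, δ | 8.0 − 5.0 = 3.0 | SAP 7.4 |
| SD, σ (read as SD of the change) | 5.0 | SAP 7.4 |
| α | 0.05, two-sided | SAP 7.4 and 7.2 |
| Target power | 0.80 | SAP 7.4 |
| Test | ANOVA on net changes; with two groups, the two-sample t-test | SAP 7.2 |
| Allocation | 1:1 | Protocol 3 |
| Evaluable n per group | 25 | SAP 7.4 |

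**Step 1. Try to reproduce 25 per group.** Normal approximation:

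n per group = 2 (1.960 + 0.842)² σ²/δ² = 2 × 7.849 × 25/9 = 43.6, so 44.

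With the noncentral t distribution, n = 44.6, so 45 per group and 90 in total (power 0.795 at 44 and 0.804 at 45). The stated 25 is not reproduced.

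**Step 2. Power at 25 per group.** The standard error of the difference is 5.0 × √(2/25) = 1.414, so the noncentrality is 3.0/1.414 = 2.121. The critical value is t(0.975, 48 df) = 2.011.

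- Noncentral t: power = 0.547.
- Normal approximation: Φ(2.121 − 1.960) = 0.564.

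**Step 3. Would another reading give 25?**

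| Reading | Result |
|---|---|
| One-sided α = 0.05 | Power 0.672 at 25 per group; 36 per group needed |
| 50 taken as the number per group | Power 0.844, but the text says 25 in each group |
| SD 5.0 is for the raw score, change analysed | SD of change = 5.0 × √(2(1 − r)); must fall to 3.71, so r ≈ 0.72 between baseline and follow-up |
| SD 5.0 is for the raw score, baseline-adjusted model | Residual SD = 5.0 × √(1 − r²); r ≈ 0.66 to 0.67 needed |
| One-sample or paired t-test, δ 3.0, SD 5.0 | n = 23.8, so 24; power 0.821 at 25 |

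Only the last of these lands near 25 without adding an input that the documents lack. It does not fit the planned comparison: the 3.0 points exist only as a difference between two independent groups, while the within-group paired tests in SAP 7.2 concern changes of 8.0 or 5.0.

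**Step 4. What 25 per group can deliver.**

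- Difference detectable with 80% power at SD 5.0: 4.04 points (standardized 0.809).
- SD needed for 80% power at 3.0 points: 3.71.
- Expected 95% CI half-width: 2.011 × 1.414 = 2.84 points, almost as wide as the planned effect.

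**Step 5. Effect of losses.** The documents give no loss rate, so the rates here are assumptions.

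| Assumed loss | Evaluable per group | Power |
|---|---|---|
| None | 25 | 0.547 |
| 10% | 22 to 23 | 0.494 to 0.512 |
| 20% | 20 | 0.456 |

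**The case against.** Four points can be made for the plan.

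First, the SD is not labelled. If it belongs to the raw score, a baseline to follow-up correlation of about 0.72 would bring 25 per group to 80% power. That is arithmetically true, but the SD follows directly after two decreases, no correlation is stated anywhere, and a correlation below 0.5 would make the SD of change larger than 5.0 and the power lower still. What stands is that the 55% is conditional on the change-score reading and should be stated so.

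Second, the documents name no formula, and the sentence about the computer analysis ends in a colon with nothing after it, so output may have been lost there. This stands as a caution about cause: use of a one-sample formula is a plausible explanation, not an established one. The failure to reproduce does not depend on it, and no missing output could make these inputs give 25 under a standard two-group test.

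Third, the section openly calls the number arbitrary, and a size set by feasibility is legitimate. It would be a full answer if the section stopped there. It does not: it goes on to claim 80% power for the same number.

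Fourth, the error neither biases the estimate nor inflates the type I error, and SAP 7.2 already promises 95% confidence intervals. Both are true. The harm lies in a false power claim and a high chance of missing a real effect.

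**Conclusion.** The concern holds. Under the stated inputs, 80% power needs 45 evaluable patients per group against 25 planned, a shortfall of 20 per group. Power at 25 per group is about 55%, so the type II error for the planned effect is about 45% (1 − 0.547) rather than the implied 20%. This rests on reading SD 5.0 as the common SD of the change score, on two-sided testing at 0.05, and on no loss of patients; with losses, 55% is the ceiling. Because the false figure concerns the primary endpoint, it must be corrected.

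**What to change.** Rewrite SAP section 7.4 as follows:

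1. Label the SD as that of the change from baseline, and give its source.
2. State that with 25 evaluable patients per group, SD 5.0 and two-sided α = 0.05, power for a 3.0-point difference is about 55%, and that 80% power is reached at a true difference of about 4.0 points.
3. Say plainly that the number was set by feasibility, if that is so, and remove the statement that it results from an 80% power calculation.
4. Delete the sentence tying 50 patients to statistical significance.
5. State an expected loss rate and the power that remains after it.
6. Add that a non-significant primary result will be interpreted through its 95% CI, expected to be about ±2.8 points, and not as evidence of no effect.

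This costs SAP wording and a less favourable stated power; it needs no extra patients. It corrects the claim but does not raise the power. If the sponsor wants 80% power for 3.0 points under these assumptions, the trial needs 90 evaluable patients plus an allowance for loss. That is a separate decision.
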